4.3.2 Functional Assays of Angiogenesis

Commercial angiogenesis assays will also be performed to evaluate the angiogenesis stimulating ability of paired wound exudate specimens.

4.3.3 Other First Line Assays

- PAI-1, lactotransferrine, S100A9, Annexine 1, AGEs (advanced glycation end-products)
- Markers of oxidative stress-alantoinuric acid ratio, protein carbonyl content
- Plasminogen activators - uPA, tPA

4.3.4 Second Line Assays

These tests will be performed if the sample volume is adequate.

- Proteolysis – MMP2, MMP9, TIMP1, TIMP2
- Angiogenesis – VEGF, bFGF
- Inflammation – IL1 (α And β), IL6, TNFα
- Fibrosis – TGFβ1
- SERPINB4,
- SERPIN D1,
- Lipocaline 2,

- IFN gamma

Comprehensive metabolic profile will be attained in ulcer fluid at the initial assessment. Changes in this profile over the subsequent assessments will highlight the metabolic response of ulcer healing. Using the chemometric software and multivariate statistical methods, potential biomarkers of ulcer healing will be identified. The changes in metabolic picture will also be correlated with the changes other mediators (PAI-1, lactotransferrine, S100A9, Annexine 1, AGEs, markers of oxidative stress, MMPs, cytokines, growth factors) to elucidate the pathogenesis of chronic venous ulcer formation. Moreover, the effect of Urgostart® dressing on the potential biomarkers of non-healing ulcer will help us to predict the treatment response.

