1.1 Objectives

We seek to further examine the biology of chronic venous ulceration. Our rationale for this study is:

1. Can we effectively predict from biological markers in whom standard therapy will not culminate in wound healing?
2. Can potential therapeutic targets be identified?
3. What changes occur in the biological profile of a chronic venous ulcer over various points in time?

Our belief is that the potential benefits of this study to wider healthcare community may be in effectively stratifying patients with chronic venous ulceration by risk of treatment failure. This may allow resources to be concentrated on high risk patients.

In addition, identifying therapeutic targets may in the future reduce the proportion of patients in whom standard treatment fails or ulcers recur.

Study of the same patients over time will help us understand the process of healing in chronic venous ulceration and determine the differences in patients who ultimately heal versus those who do not.

2. Eligibility and Inclusion

- Forty patients to be recruited from Vascular Surgery Clinics at Imperial College NHS Trust, and Cambridge University Hospitals NHS Foundation Trust.
- Male or female over the age of 18 years
- Chronic venous ulceration – Defined as wound of greater than four weeks in duration between the foot and the ankle with an Ankle Brachial Pressure Index greater than 0.85.
- Ulceration present for at least four weeks.
- Colour venous duplex evidence of chronic venous insufficiency showing either reflux or obstruction.

3. Exclusion Criteria

- Acute infection in the studied lower limb within the last four weeks
- History of malignancy in the lower limb to be studied
- History of connective tissue disease

- Patients on medications that can cause immunosuppression – Corticosteroids, chemotherapy or radiotherapy for cancer and recombinant immunological medications.

4. Study Design and Methodology

Forty patients who fulfil the criteria for the study will be recruited from Vascular Surgery clinics in hospitals under the auspices of Imperial NHS Trust in London and Cambridge University Hospitals NHS Foundation Trust in Cambridge.

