4.3 Proposed Analyses

These assays would be performed on ulcer fluid, urine and blood samples collected at the initial and each subsequent assessment.

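### Objective 1 is prediction of treatment failure, but no analysis ties week-0 or declared-landmark markers to healing by week 20, so a marker of current ulcer size could be put forward as a predictor

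*Combined protocol and SAP*

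**What the plan says.** Section 1.1 sets two separate questions. Objective 1 is prognostic: "Can we effectively predict from biological markers in whom standard therapy will not culminate in wound healing". Its intended use is "effectively stratifying patients with chronic venous ulceration by risk of treatment failure". Objective 3 is descriptive: "What changes occur in the biological profile of a chronic venous ulcer over various points in time". The same section also aims to "determine the differences in patients who ultimately heal versus those who do not", without saying when the markers in that comparison are measured.

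The analysis text does not carry this separation forward.

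- **Section 4.3** covers every visit: "These assays would be performed on ulcer fluid, urine and blood samples collected at the initial and each subsequent assessment".
- **Section 4.3.1** selects biomarkers from the full metabolite list and names no time point.
- **Section 4.3.4, closing paragraph,** begins with an ulcer-fluid profile at the initial assessment and continues "Changes in this profile over the subsequent assessments will highlight the metabolic response of ulcer healing". The next sentence is "Using the chemometric software and multivariate statistical methods, potential biomarkers of ulcer healing will be identified". Neither the visit nor the outcome for that step is given.
- **Section 4.5** names survival analysis for healing, univariate analysis for the assays and multivariate models for the metabonomic data. It does not connect any marker to the healing outcome.

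Section 4.1.2 sets visits at weeks 1, 2, 4, 8, 12 and 20 after the initial assessment, with digital planimetry at each.

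**The concern.** Stratifying patients by risk requires information available when the decision is made: at the start, or at an early fixed time while the ulcer is still open. A marker can differ between eventual healers and non-healers at a later visit simply because the healers' ulcers are already smaller. Such a marker describes the state of healing. It may have no value at week 0 and may add nothing to a tracing of the wound.

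With seven visits to week 20, three sample types and a full metabolite list, leaving the predictor time open also allows the visit to be chosen after the results are seen. Later visits favour state markers. At stake is the aim that carries the study's clinical rationale, namely directing resources to patients at high risk.

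**Working it through.** **Text check.** A prediction analysis needs a time at which predictors are measured, an outcome, and a model joining them.

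| Section | Predictor time | Outcome | Link between them |
|---|---|---|---|
| 1.1, Objective 1 | none | failure of standard therapy | none |
| 4.3 | all visits | none | none |
| 4.3.1 | none | none | software-based selection |
| 4.3.4, closing paragraph | baseline profile and later changes | ulcer healing, undefined | multivariate methods, visit not stated |
| 4.5 | none | healing, by survival analysis | none |

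No row is complete, and none adjusts for ulcer area.

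**Figures in the documents.** The plan gives no power, effect size or healing rate, so there is no figure to reproduce. From the documents come 40 patients (section 4) and the visit weeks (section 4.1.2). Every other input below is an assumption.

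**Model A.** Relative area at week *w* is exp(−*r·w*). The rate *r* is log-normal with median 0.12 per week and log-SD 0.9. An ulcer counts as closed below 10% of its baseline area. The marker is the remaining fraction plus noise, with noise SD = SD(fraction at week 8) × √(1/ρ² − 1) for ρ = 0.3, 0.5 or 0.7. At week 0 every fraction equals 1, so the marker carries no information.

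An ulcer is closed by week *w* when *r* > ln(10)/*w* = 2.303/*w*. The share closed is therefore 1 − Φ[ln(2.303/(0.12*w*))/0.9]:

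- week 4: 1 − Φ(1.74) = 4%
- week 8: 1 − Φ(0.97) = 17%
- week 12: 1 − Φ(0.52) = 30%
- week 20: 1 − Φ(−0.05) = 52%

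Mean AUC for failure at week 20, over the three values of ρ:

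| Marker used | AUC |
|---|---|
| Week 0 | 0.50 |
| Week 4 | 0.63–0.83 |
| Week 8 | 0.65–0.86 |
| Mean change, weeks 1–12 | 0.61–0.78 |
| Change to week 4, ulcers open at week 4 (about 38 of 40) | 0.59–0.75 |
| The same, current area removed | 0.50 |

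Repeat runs agreed to about 0.01. The last two rows matter for the remedy. Restricting to open ulcers does not stop a pure state marker from passing as a predictor, but accounting for measured area does.

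**Model B.** The assumptions differ: 50%, 60% or 70% healed by week 20, log-SD 0.8, closure below 5%, and samples from open ulcers only before week 20. Change from baseline correlates 0.5 or 0.7 with log area at week 12. There were 2,000 cohorts of 40 per scenario, with a Mann-Whitney test of failures against healers.

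| Week | AUC | Share with p < 0.05 |
|---|---|---|
| 0 (value) | 0.50 | 4–6% |
| 1 (change) | 0.54–0.60 | 7–15% |
| 2 (change) | 0.58–0.67 | 13–38% |
| 4 (change) | 0.64–0.75 | 30–72% |
| 8 (change) | 0.69–0.81 | 47–88% |
| 12 (change) | 0.71–0.82 | 39–83% |

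By week 12 only about 10 eventual healers still have an open ulcer to sample.

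**Precision of a week-0 analysis.** The Hanley-McNeil variance is [A(1−A) + (n_f−1)(Q₁−A²) + (n_h−1)(Q₂−A²)]/(n_f n_h), where n_f and n_h are the numbers of failures and healers, Q₁ = A/(2−A) and Q₂ = 2A²/(1+A). For A = 0.70, Q₁ = 0.5385 and Q₂ = 0.5765.

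- 20 failures, 20 healers: (0.21 + 19×0.0485 + 19×0.0865)/400 = 0.00694. SE = 0.083, 95% CI 0.54–0.86.
- 12 failures, 28 healers: (0.21 + 11×0.0485 + 27×0.0865)/336 = 0.00916. SE = 0.096, 95% CI 0.51–0.89.

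**The case against.** The strongest reply is that the plan commits no error in so many words. Section 4.3.4 collects a baseline profile and does not exclude it from biomarker identification. Change over time is a proper analysis for Objective 3, and a biomarker of healing is not the same thing as a predictor of failure. All of this stands.

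A reader might infer that later-visit markers will be reported as predictors. The documents do not say so. The one use of the word predict in section 4.3.4 concerns response to the dressing introduced at week 20, which is a different phase. The text supports only that such reporting could happen, because nothing separates the two uses.

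A reader might also infer that any marker measured after week 0 is the outcome measured twice. That does not fit early visits. In Model A, 96% of ulcers are still open at week 4, so separation there is a forecast from early trajectory, and a declared early landmark is valid. The fair question at week 4 is whether the marker adds anything to measured area.

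It is also uncertain whether samples taken after closure would enter the comparison. A closed ulcer yields no fluid. Section 4.6 lists blood and urine at weeks 1 to 12 without an exception for healed ulcers, but section 4.1.3 can be read as earlier completion.

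Finally, the simulated marker is built to follow ulcer area, so it must separate the groups. The simulations show what the plan would let through. They do not show that such markers exist in these samples.

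**Conclusion.** The point holds as a gap in the plan. Objective 1 has no stated predictor time and no analysis linking week-0 or landmark markers to healing by week 20. The only visit-linked account of healing biomarkers follows a sentence about later change, so a state marker could be presented as a predictor of failure.

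Under the assumptions shown, a marker with no week-0 information reaches an AUC of 0.63–0.83 at week 4 and 0.65–0.86 at week 8. A second model with different assumptions gives 0.64–0.75 and 0.69–0.81. The direction is the finding; the exact values depend on assumed healing rates and correlations.

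The point falls short of critical. This is an exploratory cohort of 40 looking for potential biomarkers, and the week-0 samples needed for a sound analysis are already planned.

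**What to change.** Add to section 4.5, in substance:

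- **Objective 1, primary.** Week-0 marker values are related to time to healing up to week 20, adjusted for baseline ulcer area.
- **Objective 1, secondary.** In patients whose ulcer is still open at week 4, week-0 values and change to week 4 are used to predict healing between weeks 4 and 20, adjusted for ulcer area at week 4 and its change from week 0.
- **Objective 3.** Later samples, and any sample taken after closure, are used here only and are described as markers of healing state.

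The change requires wording only. The samples and planimetry are already scheduled, so no visit or assay is added. The price is that fewer samples feed Objective 1 and apparent accuracy will be lower. Estimates in 40 patients will also be imprecise, and the report should say so with confidence intervals.

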In summary, this study is a prospective cohort study of patients with venous leg ulceration with samples of blood, urine and venous leg ulcer fluid collected over multiple time points over an initial twenty-week period with standard treatment for leg ulceration. In patients not healed fully at twenty weeks, they will be offered an Urgostart® dressing and further assessments carried out to the end of follow up at twenty-eight weeks.

The study will take place between August 2013 and February 2015.

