4.1.3 Week Twenty – Special Arrangements

If the ulcer has healed by week 20 then the patient will have completed the study. If the ulcer has not healed, the patient's standard of therapy (compression bandaging) will be complemented by the use of an Urgostart® dressing. This product will be used within its licence.

These patients will be followed up to a total of 28 weeks. Assessments as described above will be repeated at weeks 21, 22, 23, 25 and 28. These assessments will be undertaken to detect changes in the microenvironment of the wound in response to a new treatment.

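### Biomarker change in weeks 20–28 is called an effect of, or response to, Urgostart, but that phase has no concurrent comparison and only unhealed patients enter it

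*Combined protocol and SAP*

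**What the plan says.** Section 4 describes a single prospective cohort of forty patients, with samples "collected over multiple time points over an initial twenty-week period with standard treatment for leg ulceration".

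Section 4.1.3 splits the cohort at week 20. For one group, "If the ulcer has healed by week 20 then the patient will have completed the study". For the rest, the "standard of therapy (compression bandaging) will be complemented by the use of an Urgostart® dressing", with further assessments at weeks 21, 22, 23, 25 and 28. The purpose given for those visits is causal: "These assessments will be undertaken to detect changes in the microenvironment of the wound in response to a new treatment".

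The closing paragraph of section 4.3.4 goes a step further: "the effect of Urgostart® dressing on the potential biomarkers of non-healing ulcer will help us to predict the treatment response". The same paragraph says of the profile in general that "Changes in this profile over the subsequent assessments will highlight the metabolic response of ulcer healing".

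Section 4.5 plans univariate analysis for the assays and multivariate models for the metabonomic data. It names no contrast for weeks 20–28 and puts no limit on what may be attributed to the dressing.

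**The concern.** To call a change in a marker an effect of the dressing, one needs to know how the marker would have moved in the same patients over the same eight weeks on compression alone. The plan has no source for that. No unhealed patients are kept on compression alone for comparison, and no historical or external series is named.

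The prediction claim has the same gap. A week-20 marker associated with healing by week 28 may simply identify ulcers that were going to heal under compression. Without unhealed patients who did not receive the dressing, a prognostic marker cannot be told apart from one that predicts response to it.

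At stake is what may be reported. Followed as written, the protocol would support a claim that Urgostart altered wound biology, or that certain markers predict who responds to it, when the design can show only what happened after the dressing was added.

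**Working it through.** The plan states no figure on this point (no alpha, power, SD, drift or healing rate), so there is nothing to reproduce. The check is first a reading of the text, then two illustrations with assumed inputs.

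**1. Who is observed after week 20**

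| | Healed by week 20 | Unhealed at week 20 |
|---|---|---|
| Followed in weeks 20–28 | no | yes |
| Treatment in weeks 20–28 | not observed | compression plus Urgostart |
| Concurrent comparison | none | none |

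Everyone in the phase has been selected on outcome, and all are to receive the same addition at the same time point. Section 4 says the dressing is offered, so some patients may decline. No follow-up or analysis is described for them, and they would be a self-selected group.

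**2. Whether the plan itself expects change without the dressing**

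It does. Objective 3 in section 1.1 asks "What changes occur in the biological profile of a chronic venous ulcer over various points in time", and section 4.3.4 reads change over the follow-up assessments as the metabolic response of healing. Without a comparison, the same kind of movement cannot be natural healing before week 20 and a dressing effect afterwards.

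**3. Illustration: drift alone, no dressing effect**

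- Assumed: 40% to 75% heal by week 20. Patients entering the phase: 40 × 0.60 = 24 down to 40 × 0.25 = 10.
- Assumed: a paired t-test of change from week 20 to week 28, two-sided 5%. Section 4.5 names no test.
- Assumed: mean drift d, in units of the SD of the paired change.
- Rejection probability: P(|T| > t(0.975, n−1)), where T is noncentral t with n−1 degrees of freedom and noncentrality d√n.

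| d | n = 10 | n = 24 |
|---|---|---|
| 0 | 0.050 | 0.050 |
| 0.1 | 0.059 | 0.076 |
| 0.3 | 0.136 | 0.291 |
| 0.5 | 0.293 | 0.650 |

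For d = 0.3 the noncentrality is 0.3 × √10 = 0.95 and 0.3 × √24 = 1.47, giving 14% and 29%. The 95% CI half-width for mean change, t(0.975, n−1)/√n, is 0.72 SD of the change at n = 10 and 0.42 at n = 24.

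**4. Illustration: does the weeks 0–20 series help?**

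The 12 sampling visits are weeks 0, 1, 2, 4, 8, 12 and 20 before the dressing and weeks 21, 22, 23, 25 and 28 after it. Assumed: independent errors of SD 1 and complete data. For each patient, fit an intercept, a slope, and a change of level and of slope at week 20, then test the mean level change.

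- Simple change (week 28 minus week 20): SD per patient √2 = 1.41. Level term: SD per patient 1.17.
- Abrupt step of 1 SD: power for n = 10 / 24 is 0.51 / 0.91 for simple change and 0.67 / 0.98 for the level term.
- Steady drift of 1 SD per 20 weeks and no step: over 8 weeks the drift is 8/20 = 0.4 SD, or 0.4/1.41 = 0.28 SD of the change. Simple change rejects 13% / 26%. The level term stays at 5%, because the fitted slope absorbs a straight-line trend.

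Using the earlier series therefore protects against a straight-line trend and loses no power in this setting. It does not undo the selection of patients as unhealed at week 20.

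**The case against.** The strongest reply is that this is a 40-patient exploratory cohort. None of the three objectives in section 1.1 concerns Urgostart efficacy, section 4.3.4 speaks only of potential biomarkers and of helping to predict, and no endpoint or sample size depends on the claim. This stands as a limit on scope. It does not remove the point, because neither sentence is labelled exploratory and both use the language of cause.

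A second reply is that each patient serves as their own control. The earlier measurements do exist and are useful, as the last illustration shows, but section 4.5 does not plan to use them in this way. They are also not concurrent.

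A third reply is that every magnitude above is assumed. That is correct. The results run from near 5% to 65% depending on the drift chosen, so they show a mechanism and do not estimate this study's error rate.

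A reader might infer that the dressing response is the sole reason for the five visits after week 20, so that those visits lose their purpose. The documents do not support this. Section 4.3 applies the assays at every assessment, section 4.3.1 wants a profile through healing or failure to heal, and section 1.1 asks about change over time and about patients who ultimately heal or do not. All of these cover weeks 21–28 descriptively.

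**Conclusion.** The point holds as a limit on a secondary inference. The design can describe change after Urgostart was added. It cannot attribute that change to the dressing, nor show that a marker predicts response to it. This conclusion rests on the text alone and needs no assumed number. The size of any resulting bias is unknown.

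A reader might go further and conclude that the study's main aims are compromised. They are not. Objective 1, "Can we effectively predict from biological markers in whom standard therapy will not culminate in wound healing", rests on weeks 0–20 under standard treatment and is untouched. A reader might also infer that healing on compression will be pooled with healing after the dressing in the survival analysis. Section 4.5 does not say so; the horizon of that analysis is a separate missing detail and no part of this point.

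The point should be fixed: it is narrow in scope, clear in the text and cheap to correct.

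**What to change.** 1. **Section 4.1.3.** Replace the closing words about response to a new treatment with: *exploratory change after Urgostart was added*.
2. **Section 4.3.4, closing paragraph.** Make the same replacement for the phrase that calls the change an effect of the dressing. State that the change cannot be attributed to Urgostart. Label any association between markers and later healing as exploratory and prognostic under the combined treatment. Apply the same limit to the metabonomic results.
3. **Section 4.5.** Name the week 20–28 analysis: within-patient change from week 20 with a 95% CI, and the number of patients contributing at each visit for wound fluid, blood and urine (a healed ulcer yields no fluid, so these numbers will differ). Report with it a within-patient model that uses the weeks 0–20 series already collected, with a change of level and of slope at week 20 and its assumptions stated. Say that neither analysis removes selection at week 20 and that neither supports a causal claim.

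The cost is a weaker statement about the dressing and a little more analysis. Visits, samples and care do not change. Precision will be low with so few patients, and confounding by time and selection remains, which is why the wording has to change as well as the analysis.

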4.4 Data Handling and Record Keeping

4.4.1 Clinical Data

The initial assessment comprising history, examination, routine blood investigations, colour venous duplex result, venous clinical severity score, CEAP classification and assessment of wound status shall be recorded onto a standard document <clinical data document v2>. Subsequent assessments shall be recorded onto <follow up clinical data document v1>.

Clinical data shall be placed into a computerised database and each patient will be given a unique study identifying number. Clinical data documentation will be placed into the study master file.

Unique identifying numbers will be held at Imperial College and at the relevant clinical sites.

The study master file will be kept at the secure vascular clinical research office at Imperial College's Charing Cross Campus.

4.4.2 Sample Labelling and Storage

Samples will be marked with the patient's unique identifying number and a suffix to the sample will be added as per the specimen type.

Blood serum	B
Urine	U
Wound fluid – Occlusive dressing	fX
Wound fluid – Filter disc	fN
Filter disc for analysis	fW

Prior to analysis, all samples will be stored in a secure freezer at the Section of Computational and Systems Medicine, South Kensington Campus Imperial College London at -80 degrees Centigrade.

